Title:

The effect of audiovisual aids on perioperative stress response, pain and overall experience – a randomized controlled pilot study (AVA Pilot)

NCT# 02506673

Date: 9/18/19

Title:

The effect of audiovisual aids on perioperative stress response, pain and overall experience – a randomized controlled pilot study (AVA Pilot)

What is the condition or intervention to be studied?

The effect of personal audiovisual equipment (audio/video goggles) on perioperative stress, pain and overall experience in patients undergoing ambulatory meniscectomy under spinal anesthesia.

What is/are the research question(s)/specific aim(s)?

- 1) Evaluate the feasibility of the use of personal audiovisual equipment in patients undergoing meniscectomies under spinal anesthesia
- 2) Determine outcome estimates of the use of this equipment on stress levels using skin conductance measurement methodology, request for further sedation, postoperative pain levels and analgesic consumption, time to discharge readiness, and overall patient satisfaction
- 3) Collect thus far unavailable data on the stress response to perioperative stresses (such as IV insertion and spinal placement) in order to allow for power analyses for future studies

What is/are the hypothesis(es)?

- 1) The perioperative use of personal audio visual aids is feasible in the ambulatory surgical arena for meniscectomies under spinal anesthesia
- 2) The use of the audiovisual aid leads to a reduction in perioperative stress, less need for sedatives, lower postoperative pain levels and increased patient satisfaction comparable or superior to a more traditional sedation approach.

Primary outcome will be number of skin conductance responses per second (SCR/sec) and amplitude of skin conductance responses averaged over time in 5 minute intervals and at key time points such before, during and after insertion of an IV, discussion with surgeon, anesthesiologist, immediately before leaving the holding area, immediately after entering the OR, during application of monitors, before and after administration of sedatives, before, during and after spinal insertion, incision, immediately prior to leaving the OR, after arrival at PACU and monitors are placed, before discharge.

Identify and define the secondary outcome(s) and when they will be measured

- Heart rate, blood pressure and respiratory rate absolute and percent change
- Number of requests of additional sedation

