- NRS levels in PACU until discharge and day after surgery

- narcotic consumption in PACU and cumulative over 24 h after PACU discharge pre (after consent) and postoperative (before discharge) anxiety level (State Trait Anxiety Inventory)
- patient satisfaction (Heidelberg Peri-Anaesthetic Questionnaire) in PACU upon spinal resolution
- patient feedback (CSQ8) in PACU upon spinal resolution provider feedback (form sent to providers at end of surgery day)
- Request for sedation/termination of AVA
- complications (headache, transient neurologic symptoms, nausea and vomiting, ...)

Explain why these research questions are being asked:

Little is known about perioperative stress responses and possible anxiety mitigating factors like audiovisual aids or even. IV sedation. Most studies use surrogate markers and retrospective questionnaires, not based on real time gathered data. With skin conductance measurements the sympathetic discharge can be evaluated down to fractions of a second and enables us therefore to continuously monitor stress responses as skin conductance responses/per second during the perioperative management.

What is the background of the topic that you believe is important for the reviewer to know in considering this protocol, including prior studies by this research team. Describe strengths and deficiencies of prior studies; explain how this study fits in. Include references.

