anesthesiologist with ephedrine, beta blockers or other medications as indicated. Because intraoperative administration of ketorolac, dexamethasone, and periarticular prednisone and morphine could affect pain management, we will record information (dose, amount) about these medications.

Equipment will be removed in the PACU at the patient's request or upon spinal resolution. After spinal resolution, patients will complete the Heidelberg Perianaesthetic Questionnaire. If patients are randomized to the audiovisual equipment group, they will also provide feedback regarding their experience with the audiovisual equipment when they complete the CSQ8 questionnaire. Providers will also receive a survey about the audiovisual equipment at the end of the surgery day.

On POD 1, patients will report their opioid consumption and pain level since discharge.

Data will be collected:

Day of Surgery Preoperatively: from chart and patient interview

- a. Patient demographics – date of birth, race, ethnicity, gender, education level, prior surgeries
- b. State-Trait Anxiety Inventory (STAI) score
- c. NRS pain scores at rest
- d. Start time of Zeiss and HappyMed System audiovisual aids

PACU: from chart and patient interview.

- a. Anxiolytic, hemodynamic and opioid medication consumption (Also recording intraop administration of ketorolac, dexamethasone, and periarticular prednisone and morphine)
- b. End time of Zeiss and HappyMed system audiovisual aids (start and end times will be used to calculate total viewing time)
- c. Type of movie/program viewed on Zeiss and HappyMed System audiovisual aids
- d. NRS pain scores at rest
- e. STAI score
- f. Patient satisfaction (Heidelberg Perianaesthetic Questionnaire score)
- g. Patient feedback regarding use of audiovisual equipment (if randomized to that group)
- h. Provider feedback regarding use of audiovisual equipment (survey sent via email at end of surgery day)

Continuous Throughout Hospital Stay*: MedStorm Stress Detector

- a. Skin Conductance responses per second
- b. Amplitude of skin conductance responses
- c. Heart rate
- d. Blood pressure
- e. Respiratory rate
- f. Complications

Postoperative Day 1: patient interview

- a. NRS pain scores at rest
- b. Opioid medication consumption

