**Certain time points will be flagged in the recordings: before, during and after insertion of an IV, discussion with surgeon, anesthesiologist, leaving holding area, entering OR, application of monitors, administration of sedatives, before, during and after spinal insertion, incision, leaving OR, entry to PACU, resolution of spinal*

NOTE: After conducting the interim analysis and plotting the skin conductance data, we have determined that the graphs are not consistent enough to draw any conclusions. Given the technical difficulties we have encountered with the MedStorm Stress Detector, as well as the labor intensity associated with it, we have decided that we will no longer use it from patient 14 on. We will not mark hand movements, as this data was used to understand the skin conductance data. We will continue to enroll patients to complete this pilot/exploratory study, as the other secondary outcomes in particular, the surveys could provide valuable information. Patient satisfaction questionnaires will be the priority in our data analysis the "new primary outcome."

When the data will be collected?

Data will be collected on the day of surgery in the holding area, during the procedure, in the PACU until discharge, and on post-operative day 1

The following source will be used:

- Medical Records
- Patient
- No Private Office Charts Please specify which private office:
- No Registries

Sample Size and Data Analysis

Patients will be randomly assigned to one of two groups each composed of 15 patients. A computer generated randomization table will be generated by a statistician. A concealed allocation randomization schema will be used with randomization to occur after the patient consents to be in the research study. This is an un-blinded study group assignment is not concealed from the patients and the treating physicians.

1. Audiovisual equipment (Zeiss Cinema ProMED; HappyMed System) in the holding area OR and PACU + 2 mg Midazolam upon arrival in OR
2. Traditional sedation with 2 mg midazolam upon arrival in OR (control)

Phone follow ups, survey administrations and the use of the audiovisual device are not standard of care. The Department of Anesthesiology Research and Education Fund will cover the associated costs.

Instruments and questionnaires to be used on this study:

- CSQ 8
- State-Trait Anxiety Inventory

Describe any risks to participants in the Placebo or No-Treatment Arm of the study:

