There are no known risks at this time to participants in the no-treatment arm of the study.

Provide a scientific or ethical justification for using a Placebo or No-Treatment Arm:

This is considered a desirable characteristic of randomized controlled trials. Since the protocols for both groups are otherwise identical, any differences between the groups may be attributed to whether or not patients are using the audio visual aid.

Sample size and data analysis:

Is this is a case series based only on the patients available using descriptive statistics in lieu of a sample size calculation?

Yes

Data Analysis:

We will provide means/medians with SD or IQR as per distribution and differences with 95% CI for all outcomes.

We would like to undertake an interim analysis to assess the overall quality of the skin conductance data collected thus far by the MedStorm Stress Detector. Data will be considered of reasonable quality if there is limited variability in skin conductance values over very small periods of time (i.e., a few seconds or less) in the absence of disruptive stimuli, such as hand movements.

We may also compare the range of values found in our data to those reported in previously published studies that used the MedStorm Stress Detector. This is another way in which we can check the quality of our measurements.

Because this is a pilot study with a relatively small projected sample size, we believe it is important to perform this interim analysis to ensure that the instruments used to collect the skin conductance data a primary outcome for this pilot study are reliable.

Describe how, when, and where the consent process will be initiated:

Patients matching the inclusion criteria for this study will be identified the day before surgery. Patients will be approached about the study in the holding area on the day of surgery. Written consent for all patients will be obtained by research staff or co-investigators.

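### Preoperative NRS pain at rest is collected but has no role in the analysis of PACU and POD 1 pain, so a likely low-cost gain in precision is not used

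*Combined protocol and SAP*

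**What the plan says.** In the list headed 'Data will be collected', the preoperative items include "c. NRS pain scores at rest". The same item, "NRS pain scores at rest", appears again under PACU and under Postoperative Day 1. The secondary outcomes include "NRS levels in PACU until discharge and day after surgery", and hypothesis 2 expects "lower postoperative pain levels and increased patient satisfaction" with the audiovisual aid.

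The Data Analysis section has one rule for estimation: "We will provide means/medians with SD or IQR as per distribution and differences with 95% CI for all outcomes". It does not use the word unadjusted, but it names no covariate, change score or model, so a plain difference between arms is the natural reading.

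On size, the plan states: "Patients will be randomly assigned to one of two groups each composed of 15 patients". Stratification is not mentioned. The question whether the study is a case series "using descriptive statistics in lieu of a sample size calculation" is answered yes. No SD, target difference, power or correlation is given for NRS.

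On timing, randomization follows consent, which is taken in the holding area, and the audiovisual equipment is used from the holding area onwards. The preoperative anxiety inventory is fixed to the moment just after consent. The preoperative NRS is placed only on the day of surgery before the operation, in the same list as the start time of the goggles.

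**The concern.** When the same scale is measured before and after treatment, the earlier value often explains part of the spread in the later one. Adjusting for it removes that part from the standard error. It also corrects the estimate for whatever chance imbalance in preoperative pain arises in the one trial that is run. With 15 patients per arm and no stratification described, a noticeable imbalance is plausible.

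Aim 2 is to obtain outcome estimates, postoperative pain among them, and the study is described as a pilot that could lead to a more definitive protocol. Interval width is therefore what matters for this outcome. The study is also unblinded, so naming the covariate in advance avoids a choice made after the results are known.

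**Working it through.** **Inputs.** From the documents: n = 15 per arm and a 95% confidence level. The documents give no SD for NRS, so widths are in units of the outcome SD. The correlation rho between preoperative and later NRS is also not given; it is an assumption, shown from 0 to 0.7. There is no sample size calculation to reproduce; 2 × 15 = 30 agrees with the stated maximum enrollment.

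**Unadjusted 95% CI half-width.** t(0.975, 28) × √(2/15) = 0.748 SD.

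**Baseline-adjusted half-width** (linear regression on arm and preoperative NRS, 27 degrees of freedom):

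t(0.975, 27) × √[(2/15) × (1 − rho²) × (1 + 1/26)]

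Here 1/26 = 1/(2n − 4) is the expected variance cost of chance baseline imbalance.

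| Assumed rho | Adjusted half-width (SD) | Ratio to unadjusted | Change in width |
|---|---|---|---|
| 0 | 0.763 | 1.021 | 2.1% wider |
| 0.1 | 0.760 | 1.016 | 1.6% wider |
| 0.2 | 0.748 | 1.000 | none |
| 0.3 | 0.728 | 0.974 | 2.6% narrower |
| 0.4 | 0.700 | 0.936 | 6.4% narrower |
| 0.5 | 0.661 | 0.884 | 11.6% narrower |
| 0.6 | 0.611 | 0.817 | 18.3% narrower |
| 0.7 | 0.545 | 0.729 | 27% narrower |

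The ratio equals 1 at rho of about 0.20. At rho 0.5 the gain is equivalent to 30 / 0.884² ≈ 38 patients instead of 30.

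**Simulation check** (20,000 trials per rho, bivariate normal data). The mean half-width ratios were 1.020, 0.999, 0.972, 0.883 and 0.728 at rho 0, 0.2, 0.3, 0.5 and 0.7, in line with the formula. The simulated unadjusted half-width averages 0.74 rather than 0.748 because each trial uses its own estimated SD.

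**Spread around these averages.** The adjusted interval was the wider of the two in 80% of trials at rho 0, 60% at 0.2, 40% at 0.3 and 9% at 0.5. At rho 0 the 95th percentile was about 8% wider. Among trials with a baseline gap of at least 0.5 SD, the adjusted interval at rho 0 averaged about 6.7% wider.

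**Chance imbalance.** The SD of the difference in baseline means is √(2/15) = 0.365 SD. A gap of at least 0.5 SD in either direction has probability P(|Z| > 0.5/0.365) ≈ 0.17. At rho 0.5, a gap of 0.5 SD shifts the expected raw difference by 0.5 × 0.5 = 0.25 SD.

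**The case against.** The strongest case against is that this is an optional preference about a secondary outcome in a descriptive pilot. The plan states no hypothesis test or power target, and patient satisfaction is now the priority. Raw arm means, SDs and differences already give pain estimates. That stands, and it limits the point to a minor one. It does not remove it, because the plan already commits to "differences with 95% CI for all outcomes" and the proposal only says how two of those differences are estimated.

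Three further objections stand and shape the recommendation:

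- **The correlation may be low.** Chronic pain patients are excluded, surgery changes the source of the pain, and some PACU scores may be taken before the spinal resolves. A reader might infer that a free gain is being thrown away. The documents do not support that: below rho of about 0.2 adjustment costs precision on average, and they give no rho.
- **The cost has no 2% ceiling.** A reader might take 2% as the worst case. It is the average at rho 0; single trials can do worse, most of all when the baseline gap is large.
- **Timing and definition are open.** If the preoperative NRS is recorded after the goggles start, it is a post-treatment variable, and adjusting for it could bias a difference that is otherwise unbiased. PACU NRS up to discharge may also be several readings with no summary chosen, and the text elsewhere describes POD 1 pain as the level since discharge rather than at rest.

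The widths above also assume normal data. A bounded score with many values near 0 may behave differently, which is a reason to keep the unadjusted result alongside.

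**Conclusion.** The point holds as a minor one about efficiency. The preoperative NRS at rest has no role in the stated analysis, and prespecified adjustment is a likely low-cost way to sharpen the PACU and POD 1 pain differences. The balance is uneven: about 2% wider on average if the scores are uncorrelated, against 12% to 18% narrower at rho 0.5 to 0.6. It rests on an assumed rho, approximately normal data, complete data on 15 patients per arm, and a baseline score taken before randomization.

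A reader might also infer that the planned pain comparison is biased or invalid. It is not: randomization makes the unadjusted difference unbiased on average, and what it carries is any chance imbalance in the trial actually run.

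**What to change.** State in the data collection section that the preoperative NRS at rest used as baseline is recorded after consent and before randomization and goggle start. Then add to Data Analysis:

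*For PACU NRS at rest (one prespecified summary, such as the mean of the recorded PACU scores) and POD 1 NRS at rest, the between-arm difference will be estimated by linear regression on arm with pre-randomization NRS at rest as covariate, with 95% CI, and reported beside the unadjusted difference with its 95% CI. The baseline-to-outcome correlation will be reported for planning the later trial.*

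The two descriptions of POD 1 pain should be aligned at the same time.

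The cost is a few sentences, a fixed time for a score already being collected, one degree of freedom, and a slightly wider adjusted interval if preoperative and postoperative pain prove uncorrelated. Because the unadjusted difference stays in the report, nothing now planned is lost.
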